Statistical Methods/ Data Analysis: Refer to Section 10 for additional details.	
This is a phase II trial evaluating the safety and efficacy of ibrutinib and rituximab as primary treatment of cGVHD. We plan to enroll 35 patients on this study. Patients will be formally monitored for 12 months to evaluate for outcome and safety endpoints. All patients, responders and treatment failures, will be followed for a period of one year. The primary outcome measure will be the proportion of patients that are alive and off systemic immunosuppression therapies (IST) at 12 months following initiation of treatment. Secondary outcome measures will be cGVHD response, cumulative steroid exposure, time to discontinuation of systemic immunosuppression, requirement for second-line GVHD therapy, non-relapse and overall mortality, and safety.

Sample Size Determination	
The study will be powered to detect a clinically meaningful improvement in treatment success at 12 months post-treatment, defined as being alive and off all systemic immunosuppression. Experience from our phase II study of rituximab in the upfront treatment of cGVHD found that 56% of patients were alive and free of systemic immunosuppression at 12 months post treatment. It is hoped that under this protocol, this rate will be at least 75%. Thus we statistically formalize this study by testing the null hypothesis that p, the treatment success rate is 0.55 or less versus the alternative hypothesis that p is at least 0.75. A sample size of 35 patients gives 80% power with an $\alpha=0.05$, using the formula for a one sample binomial (one-sided) test of a proportion.

----------------------------------	--

ABBREVIATIONS

AE	adverse event
AESI	adverse events of special interest
ALT	alanine aminotransferase
ANC	absolute neutrophil count
ASCO	American Society of Clinical Oncology
AST	aspartate aminotransferase
AUC	area under the concentration-time curve
BCR	B-cell receptor
BTK	Bruton's tyrosine kinase
CLL	chronic lymphocytic leukemia
C _{max}	maximum observed plasma concentration
CR	complete response
CrCl	creatinine clearance
CRF	case report form (paper or electronic as appropriate for this study)
CT	computed tomography
CTCAE	NCI Common Terminology Criteria for Adverse Events
CYP	cytochrome P450
DMC	Data Monitoring Committee
ECOG	Eastern Cooperative Oncology Group
ECG	electrocardiogram
EDC	electronic data capture
FDA	Food and Drug Administration
GCP	Good Clinical Practice

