10.3. Sample Size Determination

The study will be powered to detect a clinically meaningful improvement in treatment success at 12 months post-treatment, defined as being alive and off systemic immunosuppression.

Experience from our phase II study of rituximab in the upfront treatment of cGVHD found that 56% of patients were alive and off systemic immunosuppression at 12 months post treatment. It is hoped that under this protocol, this rate will be at least 75%. Thus we statistically formalize this study by testing the null hypothesis that p , the treatment success rate is 0.55 or less versus the alternative hypothesis that p is at least 0.75. A sample size of 35 patients gives 80% power with an alpha=0.05, using the formula for a one sample binomial (one-sided) test of a proportion. Replacement of subjects may be possible for those who are lost to follow-up or withdraw from study before 12 months due to non-treatment related reasons, in order to ensure statistical power of the study.

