10.4. Efficacy Analysis Methods

This is a phase II trial evaluating the safety and efficacy of ibrutinib and rituximab as primary treatment of cGVHD. Efficacy and safety endpoints will be estimated according to the cumulative incidence and Kaplan-Meier methodology in the presence of competing risks. Outcomes will be compared to historical values based on the Gray's test and log rank test respectively. We plan to enroll 35 patients on this study. Patients will be formally monitored for 12 months to evaluate for outcome and safety endpoints (efficacy/safety visits at the completion of month 1, 2, 3, 6, 9, and 12). All other assessments will be done at the physician's discretion or institutional standards. All patients, responders and treatment failures, will be followed for a period of one year. The primary outcome measure will be the proportion of patients that are alive and off all systemic immunosuppression at 12 months following initiation of treatment. The primary endpoint will be estimated according to the Kaplan-Meier methodology in the presence of competing risks. Outcome will be compared to historical values based on the log rank test. Secondary outcome measures will be cGVHD response, cumulative steroid exposure, time to discontinuation of systemic immunosuppression, requirement for second-line cGVHD therapy, non-relapse and overall mortality, failure-free survival and safety. Secondary survival endpoints will be estimated according to the Kaplan-Meier methodology in the presence of competing risks, and outcomes will be compared to historical values based on the log rank test. Secondary time-to-event endpoints will be estimated according to cumulative incidence methodology, and outcomes will be compared to historical values based on the Gray's test (Gray 1988).

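### The 80% power comes from a normal approximation: with 35 patients no success cutoff gives 80% power within one-sided alpha 0.05 (exact power is 75.8%), and section 10.4 plans a different test

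*Combined protocol and SAP*

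**What the plan says.** Section 10.3 (Sample Size Determination) sets up a one-sample test of the 12-month treatment success rate p. The null hypothesis is that p, "the treatment success rate is 0.55 or less versus the alternative hypothesis that p is at least 0.75". The sample size statement is "A sample size of 35 patients gives 80% power with an alpha=0.05, using the formula for a one sample binomial (one-sided) test". The synopsis row on sample size makes the same claim: "A sample size of 35 patients gives 80% power with an" alpha of 0.05. Neither place says whether the formula is exact or approximate, and neither gives the number of successes that would reject the null.

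Section 10.4 (Efficacy Analysis Methods) defines the primary outcome as a proportion at 12 months but does not mention a binomial test. It says: "The primary endpoint will be estimated according to the Kaplan-Meier methodology in the presence of competing risks". The next sentence is: "Outcome will be compared to historical values based on the log rank test".

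**The concern.** There are two linked problems.

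First, the primary outcome is a count out of 35, so only whole-number cutoffs exist. A power figure from a smooth normal formula need not be reached by any of them. If it is not, the study's real chance of detecting a 75% success rate differs from the one stated.

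Second, the test that was sized is not the test that is planned. Section 10.3 compares a proportion with the fixed value 0.55. Section 10.4 compares outcomes with historical values by log rank. The stated power does not carry over from one to the other. With no cutoff in the plan, a result close to the boundary could be called positive or negative depending on a choice made after the data are seen.

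**Working it through.** **Inputs.** From section 10.3: p0 = 0.55, p1 = 0.75, n = 35, one-sided alpha = 0.05, stated power 80%. The normal quantiles are 1.645 (alpha) and 0.842 (power).

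**Reproducing the plan's figure.** The normal approximation uses the null variance for alpha and the alternative variance for power:

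n = [(1.645 × √(0.55 × 0.45) + 0.842 × √(0.75 × 0.25)) / (0.75 − 0.55)]² = [(1.645 × √0.2475 + 0.842 × √0.1875) / 0.20]² = 34.97, rounded up to 35.

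Power at n = 35 is Φ[(0.20 × √35 − 1.645 × √0.2475) / √0.1875] = 80.03%. This matches the stated 80%. The arcsine formula, also a large-sample method, comes close (n = 34.5, power 80.5%). A continuity correction does not match (n = 39.8, power 74.1%), and nor does a two-sided 0.05 test (n = 44.9, power 68.5%).

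**Exact binomial at n = 35.** X is the number of successes. Type I error is P(X ≥ c | p = 0.55) and power is P(X ≥ c | p = 0.75).

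| Reject if X is at least | Observed rate | Type I error | Power at 0.75 |
|---|---|---|---|
| 24 | 68.6% | 0.0729 | 0.8579 |
| 25 | 71.4% | 0.0354 | 0.7581 |
| 26 | 74.3% | 0.0152 | 0.6263 |

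The smallest cutoff with type I error at or below 0.05 is 25. Its power is 75.8%, so the type II error is 1 − 0.758 = 24.2%.

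**Does this depend on choosing the exact test?** The other common tests at the boundary give:

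- Score z-test (null variance, as in the sizing formula): at 24/35, z = (0.6857 − 0.55) / √(0.55 × 0.45 / 35) = 1.614, below 1.645. At 25/35, z = 1.954. It rejects from 25, so its true power is also 75.8%.
- Mid-p: at 24/35, 0.0354 + ½ × (0.0729 − 0.0354) = 0.054, above 0.05. It rejects from 25.
- Wald z-test (observed variance): at 24/35, z = (0.6857 − 0.55) / √(0.6857 × 0.3143 / 35) = 1.730. It rejects from 24.
- Arcsine z-test: at 24/35, z = 2 × (asin√0.6857 − asin√0.55) × √35 = 1.659. It rejects from 24.

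The last two have 85.8% power, but their true type I error is 7.3%, which breaks the stated alpha. No cutoff at n = 35 gives 80% power within 0.05.

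**How far short.** With the rule of 25 or more, power reaches 80% at a true success rate of 76.0%. The smallest n with exact power of at least 80% is 37 (cutoff 26, alpha 0.043, power 80.6%).

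**10.3 beside 10.4.** Section 10.3 tests one binomial proportion against a constant. Section 10.4 uses a Kaplan-Meier estimate and a log rank comparison with historical values, and does not say which historical data would enter that comparison. The calculation above applies only to the first.

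**The case against.** The strongest reply is that there is no arithmetic error. The plan cites a formula and never claims it is exact; the standard closed-form formula returns 35 patients and 80.03%. The shortfall is 4.2 points, it leaves type I error below nominal, and it closes at a true rate one point above the design value, which the plan itself offers as a hope ("It is hoped that under this protocol, this rate will be at least 75" percent). Part of the gap is the saw-tooth of the binomial: exact power is 78.9% at 34 patients, 75.8% at 35, 72.5% at 36 and 80.6% at 37. For a single-arm, single-center phase II study, that alone would be minor. It can also be said that 10.3 gives enough for a reader to work out the cutoff of 25.

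Most of this is fair as to size. The 80% is an approximation, not a miscalculation, and the error is conservative on false positives. It does not rescue the statement, because even the score z-test that corresponds to the sizing formula has 75.8% true power. Nor does it touch the mismatch with 10.4, which is the more important part and would remain if the power were exactly 80%. A reader can derive 25 from 10.3 only by choosing among test variants that disagree at 24 of 35, and 10.4 then points to another test altogether.

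A further fair point is that a cutoff fixed for 35 does not cover every case. Section 10.1 analyses all treated subjects and 10.3 allows replacement, so the number analysed could exceed 35. The cutoff becomes 26 at both 36 and 37.

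**Conclusion.** The concern holds. Under the one-sided binomial test that 10.3 names, held to alpha 0.05, 35 patients give 75.8% power at a 75% success rate, not 80%; the risk of missing that effect is 24% rather than 20%. Type I error at the cutoff of 25 is 3.5%, so false-positive control is sound. The log rank comparison in 10.4 is not the test that was powered, so as written the primary analysis has no stated power and no stated criterion for success. This should be fixed.

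The figures assume that exactly 35 patients are analysed, each with a known 12-month status. They do not depend on the choice of 0.55 rather than the historical 56%: against 0.56 the cutoff is still 25 (exact alpha 0.0456) with the same power.

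**What to change.** In section 10.3 and the synopsis, name the exact one-sided binomial test and state that, with 35 treated patients, the null of 0.55 or less is rejected if 25 or more are successes, with exact one-sided alpha 0.035 and exact power 76% at 0.75. Keep 0.55 as the null value.

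In section 10.4, name this same test as the primary analysis in place of the log rank comparison with historical values, so that the restated power applies to what is done. Two additions would complete it: the cutoff for other numbers analysed (26 at 36 or 37 patients), and a rule for counting patients without a 12-month status, since a binomial count needs one and a Kaplan-Meier estimate does not supply it.

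The cost is wording in three places, a less favorable stated power (76% instead of 80%) and the loss of the log rank test as the primary comparison. No additional patients are needed. If the sponsor prefers to keep 80%, 37 patients with a cutoff of 26 would give 80.6% at alpha 0.043, two patients more than planned.

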10.4. Efficacy Analysis Methods

This is a phase II trial evaluating the safety and efficacy of ibrutinib and rituximab as primary treatment of cGVHD. Efficacy and safety endpoints will be estimated according to the cumulative incidence and Kaplan-Meier methodology in the presence of competing risks. Outcomes will be compared to historical values based on the Gray's test and log rank test respectively. We plan to enroll 35 patients on this study. Patients will be formally monitored for 12 months to evaluate for outcome and safety endpoints (efficacy/safety visits at the completion of month 1, 2, 3, 6, 9, and 12). All other assessments will be done at the physician's discretion or institutional standards. All patients, responders and treatment failures, will be followed for a period of one year. The primary outcome measure will be the proportion of patients that are alive and off all systemic immunosuppression at 12 months following initiation of treatment. The primary endpoint will be estimated according to the Kaplan-Meier methodology in the presence of competing risks. Outcome will be compared to historical values based on the log rank test. Secondary outcome measures will be cGVHD response, cumulative steroid exposure, time to discontinuation of systemic immunosuppression, requirement for second-line cGVHD therapy, non-relapse and overall mortality, failure-free survival and safety. Secondary survival endpoints will be estimated according to the Kaplan-Meier methodology in the presence of competing risks, and outcomes will be compared to historical values based on the log rank test. Secondary time-to-event endpoints will be estimated according to cumulative incidence methodology, and outcomes will be compared to historical values based on the Gray's test (Gray 1988).

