In a completed phase II trial, our group tested rituximab in the upfront treatment of patients with cGVHD, and the results of this study were recently published in *Biology of Blood and Marrow Transplantation: Corticosteroid-Free Primary Treatment of Chronic Extensive Graft-versus-Host Disease Incorporating Rituximab* (Solomon, Sizemore et al. 2015). We hypothesized that the early use of rituximab would allow for more rapid discontinuation of immunosuppression while obviating the need for long courses of systemic corticosteroids, which would translate into reduced treatment-related morbidity and mortality associated with cGVHD.

Twenty-five patients (median age 56 years [range 29 – 77]) with extensive cGVHD were enrolled on a prospective phase II trial at our institution. Enrollment was limited to patients with first onset extensive cGVHD requiring systemic immunosuppression and without residual or concurrent acute GVHD. All patients received Rituximab 375mg/m² x 4 weekly doses, then one dose q3months x 4 doses. Twenty-two of 25 patients (88%) responded to treatment. Of the 22 responding patients, median time to maximum response was 161 days (range 35 – 300 days) with maximum response being complete in 21/22 patients and partial in 1 patient. Corticosteroids were used sparingly or not at all in the majority of patients. Immunosuppression was discontinued in 17 of 22 evaluable patients (77%) with median time to discontinuation of 300 days (range 138 – 488 days). With a median f/u of 27 months, estimated 2-year overall survival is 82%. Following immunosuppression discontinuation, cGVHD did recur in 7 patients after a median of 166 days (range 21-393 days), requiring reinstitution of systemic immunosuppression. When patients were analyzed 12 months following treatment initiation, 56% were alive, free of active GVHD, and off all systemic immunosuppression.

1.1.3. Targeting the Bruton's tyrosine kinase (BTK) and IL-2 inducible T-cell kinase (ITK) pathways with Ibrutinib for the treatment of cGVHD

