2. STUDY OBJECTIVE

2.1. Primary Objective

The primary objective is to evaluate the efficacy of the combination of rituximab and ibrutinib versus the historical experience with rituximab alone in the upfront treatment of cGVHD. The primary efficacy endpoint is to estimate the proportion of patients that are alive and off IST at 12 months following initiation of treatment. To meet this endpoint, patients need to remain off IST (e.g. sirolimus, tacrolimus, steroids, etc). for at least 8 weeks. The use of rituximab and ibrutinib are not considered IST for this endpoint.

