6.3. Other Systemic Immunosuppression Therapy for cGVHD

Addition of any new systemic immunosuppressant therapy (including ECP) to treat worsening cGVHD is prohibited. This will be considered a treatment failure, patient will be removed from study and treated according to institutional standard-of-care.

Any increase in the dose of methylprednisolone (or equivalent) and any resumption of treatment with methylprednisolone, after previous discontinuation, is not considered as secondary systemic therapy.

Any increase in the dose of sirolimus or calcineurin inhibitor, or resumption of treatment following discontinuation, is not considered as secondary systemic therapy, if the treatment in question was included in the immunosuppressive regimen at study initiation.

A substitution of the systemic immunosuppressant drug (e.g. tacrolimus for sirolimus) for reasons other than cGVHD progression (e.g. toxicity) may be permitted after discussion with the principal investigator and is not considered as secondary systemic therapy.

Topical therapy, including steroid creams, topical tacrolimus, oral budesonide, inhaled steroids and ophthalmic solutions are not considered as secondary therapy.

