10.2. Endpoints

10.2.1. Primary Endpoint

The primary endpoint is to estimate the proportion of patients that are alive and off all systemic IST at 12 months following initiation of treatment. To meet this endpoint, patients need to remain off IST for at least 8 weeks after discontinuing systemic immunosuppression (e.g. sirolimus). The use of rituximab and ibrutinib are not considered IST for this endpoint.

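### Sections 10.3 and 10.4 prescribe different primary analyses for the same month-12 endpoint: a one-sided binomial test against 0.55, and Kaplan-Meier with a log-rank test against historical values

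*Combined protocol and SAP*

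**What the plan says.** Section 10.2.1 defines the primary endpoint as the proportion of patients alive and off all systemic immunosuppression (IST) at 12 months, with a durability condition: "To meet this endpoint, patients need to remain off IST for at least 8 weeks after discontinuing systemic immunosuppression".

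Section 10.3 does more than justify the sample size. It reads "Thus we statistically formalize this study by testing the null hypothesis that p" is at most 0.55, against an alternative of at least 0.75, and obtains 35 patients, 80% power and alpha 0.05 "using the formula for a one sample binomial (one-sided) test of a proportion". The synopsis repeats this.

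Section 10.4, the analysis-methods section, restates the same month-12 proportion as the primary outcome. It then says: "The primary endpoint will be estimated according to the Kaplan-Meier methodology in the presence of competing risks". The next sentence is: "Outcome will be compared to historical values based on the log rank test". Later sentences assign methods to the secondary survival and time-to-event endpoints separately, so the primary endpoint has not merely been swept into a general statement.

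The historical source can be identified. Section 2.1 says: "The primary objective is to evaluate the efficacy of the combination of rituximab and ibrutinib versus the historical experience with rituximab alone". Section 1.1.2 describes that experience: 25 patients, of whom 56% were alive, free of active GVHD and off all systemic immunosuppression 12 months after starting treatment.

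**The concern.** Two different analyses are attached to one endpoint, and no section ranks or reconciles them. A statistician working from 10.4 would not run the test that 10.3 formalizes. Section 10.4 names neither the 0.55 null nor the binomial test, and for the log-rank step it leaves open the event, the censoring, the alpha, the sidedness, and whether the reference is patient records or a fixed curve or value.

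The 10.4 method also fits the endpoint poorly as written. Being alive and off IST at month 12 is a status at a fixed time, and it can reverse. In the historical study "cGVHD did recur in 7 patients after a median of 166 days (range 21-393 days), requiring reinstitution of systemic immunosuppression". Kaplan-Meier describes time to a first event. It reproduces the month-12 proportion only under particular choices, for example failure as the event with nobody censored before month 12. Section 10.4 does not state such choices.

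At stake is the only formal hypothesis in a single-arm, open-label trial. If the conflict stays, the deciding test can be chosen after the data are seen, and the stated power describes only one of the two candidates.

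**Working it through.** **Inputs.** From 10.3: p0 = 0.55, p1 = 0.75, N = 35, one-sided alpha 0.05, power 80%. From 1.1.2: 25 historical patients and 56%, which is 0.56 × 25 = 14 successes and 11 failures.

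**1. The plan's own figure.** n = [(1.645·√(0.55·0.45) + 0.842·√(0.75·0.25)) / 0.20]² = [(0.818 + 0.364) / 0.20]² = 34.97, so 35. Power at 35 by the same formula is 0.800. The 80% therefore belongs to the normal-approximation formula for the binomial test.

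**2. The 10.3 test run exactly at N = 35.**

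| Success if at least | Actual alpha (p = 0.55) | Power (p = 0.75) |
|---|---|---|
| 24/35 | 0.073 | 0.858 |
| 25/35 | 0.035 | 0.758 |
| 26/35 | 0.015 | 0.626 |
| 27/35 | 0.006 | 0.474 |

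The smallest cutoff that keeps alpha within 0.05 is 25/35. The uncorrected z-test has the same cutoff: z = 1.614 at 24 and 1.954 at 25, against 1.645. The exact one-sided 95% lower bound agrees: 0.534 at 24/35 and 0.564 at 25/35.

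**3. The 10.4 comparison read as two-sample.** Assumptions: 14/25 in the historical group, all failures recorded at month 12, no censoring, one-sided 5%. With one failure time, the log-rank statistic is z = (O − E)/√V. Here d is the total number of failures in the 60 patients, E = 35d/60 and V = 35·25·d·(60 − d)/(60²·59).

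| Trial successes | O | d | E | V | z | Log-rank p | Exact binomial p |
|---|---|---|---|---|---|---|---|
| 25/35 | 10 | 21 | 12.25 | 3.37 | −1.225 | 0.110 | 0.035 |
| 26/35 | 9 | 20 | 11.67 | 3.30 | −1.469 | 0.071 | 0.015 |
| 27/35 | 8 | 19 | 11.08 | 3.21 | −1.721 | 0.043 | 0.006 |

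On this reading 25 and 26 successes pass under 10.3 and fail under 10.4. If the true rate is 0.75, P(25 or 26) = 0.758 − 0.474 = 0.284.

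**4. The 10.4 comparison read as against a fixed value.** Same assumptions, with binomial variance n·S0·(1 − S0).

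- S0 = 0.55: z = (25 − 19.25)/2.943 = 1.954, p = 0.025 at 25/35; p = 0.053 at 24/35.
- S0 = 0.56: z = (25 − 19.60)/2.937 = 1.839, p = 0.033 at 25/35; p = 0.067 at 24/35.

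The cutoff is 25/35 either way, the same as the binomial test. The conflict in step 3 disappears.

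**5. Log-rank power, illustrative only.** Take failure as the event, proportional hazards and 35 against 25 patients. Events are 0.45·25 + 0.25·35 = 20, and the hazard ratio is ln 0.75 / ln 0.55 = 0.481. Schoenfeld power is Φ(0.731·√(20·(35/60)·(25/60)) − 1.645) = Φ(1.613 − 1.645) = 0.487. Other choices (success as the event, history at 0.56, simulation with exponential times) give 46–53% one-sided. A one-sample log-rank test against a fixed exponential curve gives 74–86%. The plan supplies none of these assumptions.

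**The case against.** **The disagreement depends on the reading.** Section 10.4 speaks of historical values, and 10.3 fixes 0.55. A reader might infer from step 3 that the two sections must lead to opposite conclusions. Step 4 shows that they need not. This objection stands, so the 28% belongs to the two-sample reading alone.

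**Overstated success is one implementation, not the text.** If the event were first stopping of IST with deaths censored, restarts would be ignored and success overstated. Section 10.4 does refer to competing risks, which suggests that deaths were meant to be handled, although ordinary Kaplan-Meier does not do that. Kaplan-Meier can also match the proportion in other ways, for example with success as the event and every non-success, including deaths, kept at risk to month 12. A reader might infer that 10.4 is certain to inflate the result; the documents do not support that.

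**Reversal by month 12 is not quantified.** IST was stopped between day 138 and day 488, and recurrence came 21 to 393 days after stopping. The ranges allow a restart as early as day 138 + 21 = 159, but section 1.1.2 does not say how many of the 7 had restarted by month 12.

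**The historical count is not like for like.** The 56% in 1.1.2 also required freedom from active GVHD, which the present endpoint does not, so 14/25 is an approximation.

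**Sidedness and alpha could be carried over from 10.3.** They could, but the event, the censoring and the form of the reference could not.

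**The 80% is not an arithmetic error.** Correct: the formula that 10.3 cites gives 35. Restating the exact power makes the decision rule explicit; it is not what resolves the conflict.

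None of this removes the conflict between the two sections.

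**Conclusion.** The concern holds as a conflict between sections. 10.3 and the synopsis formalize a one-sided binomial test of the month-12 proportion against 0.55. 10.4 assigns Kaplan-Meier and a log-rank test to the same endpoint, does not define that analysis well enough to run it, and omits the binomial test. The 80% power describes the 10.3 formula only. This must be fixed because it concerns the trial's single formal test, and that conclusion rests on the text alone.

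The size depends on an unstated choice. In a two-sample comparison with the 25 historical patients, under the assumptions of step 3, the verdict differs at 25 and 26 successes, a 28% chance at a true rate of 0.75. Against a fixed 0.55 or 0.56 the cutoffs coincide. The log-rank power figures are illustrations and carry no weight in the verdict.

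**What to change.** In 10.4, replace the Kaplan-Meier and log-rank sentences for the primary endpoint with:

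> The primary analysis is a one-sided exact binomial test of H0: p ≤ 0.55 at alpha 0.05 in all treated subjects. The observed month-12 success proportion is reported with its exact one-sided 95% lower bound (or two-sided 90% interval). Patients who die or start second-line cGVHD therapy (section 6.3) before month 12 are non-successes. Treated patients whose month-12 status is unknown stay in the denominator as non-successes; a sensitivity analysis excludes them.

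The endpoint already requires survival. On new systemic therapy for worsening cGVHD, section 6.3 already says: "This will be considered a treatment failure, patient will be removed from study". The rule for unknown status is new. It is needed because an exact test in all treated subjects cannot be run while some outcomes are undefined, and 10.3 says only that replacement may be possible.

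In 10.3 and the synopsis, state the rule at N = 35: success if at least 25/35, actual alpha 0.035, exact power 75.8% in place of 80%, noting that 80% is the normal-approximation figure.

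Any Kaplan-Meier or log-rank comparison of the primary endpoint with historical values should be labelled supportive. The secondary analyses in 10.4 can stay as they are.

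Cost: wording only, with N unchanged. The stated power falls from 80% to 75.8%, and counting unknown status as non-success lowers it further if patients are lost; the plan gives no dropout rate from which to size that.
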